7. STUDY ENDPOINTS

7.1. Primary Endpoint

• Success of epidural localization

(defined as the catheter can be inserted into epidural space successfully, no cold perception in the blocked dermatomes after the injection of anesthetic by cold sensation test, and no occurrence of inadvertent dural puncture.)

7.2. Secondary Endpoint

- The time to identify the epidural space (defined as the time of the successful localization from the first syringe attached to the Tuohy needle to the occurrence of LOR signal)
- (2) Duration of the epidural space localization procedure(defined as the time from the puncture of skin to the successful insertion of the epidural catheter)
- (3) Number of attempts

(defined as a new puncture of the skin)

(4) Number of the occurrence of false positive

(defined as the insertion of the epidural catheter is unsuccessful or the perception of cold exists in the blocked dermatomes after the injection of anesthetic by cold sensation test)

- (5) The distance from the skin to the epidural space
- (6) Number of change insertion segment

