4.1.2. Detail description of the principle of EpiFaith Syringe

EpiFaith Syringe is based on the LOR technique, which means the visual signal is triggered by the pressure change occurring at the moment the needle tip arrives the epidural space.

EpiFaith Syringe should be connected to a 16-18 gauge epidural needle to locate the epidural space. After the needle is inserted to an appropriate depth and the stylet is removed, the EpiFaith Syringe can be connected to it. The initial pressure is induced by pushing the plunger and the fixator can hold the position of the plunger to maintain the pressure.

The spring is compressed due to the initial pressure and constantly delivers force to the content in the syringe (sensing material such as air or normal saline). Because of the spring force, the ejection of the sensing material will happen when the LOR occurring, resulting in the movement of the low friction rubber. It provides a visual signal to warn the anesthesiologists that the LOR has happened, which implies that the needle tip has arrives the epidural space. The parameters of the EpiFaith Syringe can be found in Figure 3.

For more detail please see the demo video: https://tinyurl.com/y8serflu

[figure not shown]

Figure 3. The different states of EpiFaith Syringe. (a) The indicator is fully protruded and the spring is released. (b)&(c) The spring is compressed and the indicator is covered by the plunger. The fixator can help to maintain the position of the rear plunger. Therefore, even though the spring constantly applies a spring force on both indicator and the plunger, the plunger will not be pushed back.

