5.2.5. Epidural space localization procedure

Subjects will undergo the surgical procedure using epidural space localization in a medical center with appropriate facilities and by appropriately trained personnel.

Epidural space localization planning will be completed before the epidural space localization. The plan should be recorded, and the records should include surgery name, insertion segment.

During epidural space localization, the subject are in the lateral position. After cleaning and draping the area, a local anesthetic is infiltrated at the insertion site of epidural needle.

Anesthesiologist inserted the epidural needle at least 3cm to pass the subcutaneous tissue. Pull out the stylet and attach the filled EpiFaith syringe. In Group A, the EpiFaith syringe is filled with air; in Group S, the EpiFaith syringe is filled with saline. Then, push the plunger to create a continuous pressure inside the syringe. When the needle arrived the epidural space, due to LOR occurred, the piston of EpiFaith syringe will move forward. The clear visual signal can warn the operator the localization of needle tip. After the detection of LOR, the catheter will be inserted though the needle. When the catheter can protrude from the needle tip at least 3cm, which can be identified by the graduations on its surface, the test dose (2 ml of 2% lidocaine) of anesthetic will be injected. After injection for 15min, the cold sensation test will be performed, by comparing the perception of cold of alcohol sponges between the blocked dermatomes and face. The tests will be bilaterally, and repeated 3 times in 3 difference dermatomes on each side.

If the visual signal occurs but the catheter cannot be inserted to protrude the needle tip at least 3 cm, which means the false positive occurs.

If the catheter is inserted successfully and the test dose of anesthetic is injected, but the result of cold sensation test shows the perception of cold exists in the blocked dermatomes by cold sensation test and exclude the reason is due to dose and drug failure, which also means the false positive occurs.

If the inadvertent dural puncture occurs, the success of epidural localization will be recorded failed. There is no necessary to record all secondary outcome. The physician can use the traditional LOR syringe or other method to compete the procedure.

The process of epidural space localization will be simultaneously recorded by video.

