5.2.5.1. The duration and attempt of epidural localization

The designated assessments of duration and attempt of epidural space localization are defined as below:

- Success of epidural localization is defined as the catheter can be inserted into epidural space successfully, no cold perception in the blocked dermatomes after the injection of anesthetic by cold sensation test, and no occurrence of inadvertent dural puncture.
- The time to identify the epidural space is defined as the time of the successful localization from the syringe attached to the Tuohy needle to the occurrence of LOR signal.
- Duration of the epidural space localization procedure is defined as the time from the first puncture of skin to the successful insertion of the epidural catheter.
- Number of attempts is defined as a new puncture of the skin.
- Number of the occurrence of false positive is defined as the insertion of the epidural catheter is unsuccessful or the perception of cold exists in the blocked dermatomes after the injection of anesthetic by cold sensation test.
- The distance from the skin to the epidural space.
- Number of change insertion segment

[figure not shown]

Fig. 6. The definition of the outcome measurement of this study

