6.1.6. Managements of AE

The using of EpiFaith syringe will not change the managements of AEs.

Table 6. The managements of common AEs related the procedure of epidural localization.

AEs	Treatments
Post puncture headache	Supporting treatment such as rehydration, simple analgesics, opioids and anti-emetics may control the symptoms in milder cases. Generally, >85% of headaches after lumbar puncture will resolve without any specific treatment. Depending on the severity of the headache, prolonged hospital stay for better care and procedure such as blood patch may be required.
Accidental intravascular catheter placement	The intravascular catheter can either be withdrawn (1 cm at a time then flushed with saline and aspirated) until no more blood is be aspirated, or it can be totally removed and replaced.
Accidental subarachnoid catheter placement	The risk of inadvertently administering an epidural dose intrathecally. The headache may occur, and prolong hospital stay for better care and procedure such as blood patch may be required.
Bleed at needle entry area	Clean the puncture area with sterile protocol.

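### The false-positive endpoint has no dural-puncture limb, so a device signal given with the needle tip or catheter through the dura is not reliably counted as a wrong signal

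*Combined protocol and SAP*

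**What the plan says.** Section 4.1.2 gives the meaning of the visual signal: "the LOR has happened, which implies that the needle tip has arrives the epidural space". A signal given with the tip elsewhere is, on the protocol's own terms, a wrong signal.

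The false-positive count is a secondary endpoint. Section 7.2 has it "defined as the insertion of the epidural catheter is unsuccessful or the perception of cold exists in the blocked dermatomes", and 5.2.5.1 uses the same two limbs: "Number of the occurrence of false positive is defined as the insertion of the epidural catheter is unsuccessful or the perception of cold exists". Section 5.2.5 gives the operating rules. The threading rule is "If the visual signal occurs but the catheter cannot be inserted to protrude the needle tip at least 3 cm". The cold-test rule applies once the catheter is in and the test dose given: "the perception of cold exists in the blocked dermatomes by cold sensation test and exclude the reason is due to dose and drug failure".

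Primary success in 7.1 needs the catheter in the epidural space and, in addition, "no cold perception in the blocked dermatomes after the injection of anesthetic by cold sensation test, and no occurrence of inadvertent dural puncture".

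Section 5.2.5 also says that an inadvertent dural puncture makes the primary endpoint a failure and that the secondary outcomes need not then be recorded. Section 8.4 applies no imputation. Section 8.4.2 compares the false-positive count between air and saline by Fisher's exact test. Table 6 in 6.1.6 lists "Accidental subarachnoid catheter placement" among the common adverse events of the procedure.

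**The concern.** Among the secondary endpoints, the false-positive count is the one aimed directly at whether the signal was right. Its two limbs pick up signals that come where the catheter will not pass or the block does not develop. Neither limb names a signal that comes with the tip beyond the epidural space. The introduction gives avoidance of dural puncture as the reason for stopping the needle promptly, so this kind of wrong signal matters.

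Two things are at stake. First, the air-versus-saline false-positive comparison can leave out one type of wrong signal, and nothing makes the omission equal in the two arms. Second, section 8.1 says that the parameters from this trial will feed the sample size of a full-scale trial, so an understated false-positive rate could carry forward.

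**Working it through.** **Rule check.** No planned figure is at issue, so the first step is to score three cases by the text.

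| Case | Primary (7.1) | False-positive count |
|---|---|---|
| Signal; catheter will not protrude 3 cm | Not a success at that signal | 1 |
| Signal; dural puncture recognised; operator changes method | Failure | Need not be recorded (5.2.5), not imputed (8.4): missing. If the site records it anyway, neither 5.2.5 rule has been met: 0 |
| Signal with tip through the dura; catheter threads at least 3 cm intrathecally; test dose abolishes cold (assumed); puncture not recognised | Success recorded | 0 under the 5.2.5 rules |

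If the third case is recognised, it becomes a puncture case and the count is again usually missing. Removing the recording waiver alone would not settle the matter, because the 3 cm and cold-test rules would still return 0.

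The wording in 7.2 is looser than in 5.2.5. It does not mention the signal, so an unsuccessful insertion could be read to cover a puncture, but it would then also cover a puncture with no signal at all.

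**Number of subjects affected.** Inputs: n = 60 (8.1) and puncture rate p = 0.19% to 3.6% (section 1).

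- Expected punctures = n × p: 60 × 0.0019 = 0.11; 60 × 0.036 = 2.16.
- P(at least one) = 1 − (1 − p)^60: 10.8% at p = 0.0019; 88.9% at p = 0.036.

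The documents do not give the share of punctures preceded by a signal, so it is left at 0-100%.

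**Effect on the reported rate.** Assume 6 subjects with ordinary false positives and 2 other subjects with signalled punctures.

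- Count missing for the 2: 6/58 = 10.3%.
- Count recorded as zero: 6/60 = 10.0%.
- Signalled punctures counted: 8/60 = 13.3%.

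In this illustration 2 of 8 subjects with a wrong signal (25%) are left out. If none of the punctures followed a signal, none would be left out.

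**The case against.** The strongest reply is that dural puncture has its own place in the plan and need not be counted twice. This is largely right for the puncture itself. A reader might infer that the trial misses these events altogether. The documents do not support that: a recognised puncture is a primary failure compared by arm (7.1, 8.4.1), counts towards the stopping rule in 6.2, and falls under adverse-event recording and comparison (6.1.5.1, 8.5). None of these records whether the device had signalled.

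A reader might also infer that every such signal is scored as zero false positives. That is too strong. After a recognised puncture the count is normally missing under 5.2.5 and 8.4. In addition, 7.1 speaks of insertion into the epidural space, so unsuccessful insertion in 7.2 can be read to include a subarachnoid catheter. That reading is available but not secured, because 5.2.5 defines the failure by 3 cm of protrusion.

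A third inference is that the comparison would come out in favour of the worse medium. This can be constructed: ordinary false positives of 3 (air) and 5 (saline), plus 5 signalled punctures, all in the air arm. The report would show 3/25 (12.0%) v 5/30 (16.7%) if missing, against 8/30 (26.7%) v 5/30 if counted. But five or more punctures in an arm of 30 has a probability of about 0.4% at 3.6%, and about 3 in a billion at 0.19%. Fisher's test would not separate the arms under either scoring (p = 0.72 and 0.53). The primary endpoint would also penalise the air arm.

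Two further limits stand. A correct epidural signal followed by over-advancement is not a wrong signal. And the caution in 4.1.3 says that failure to build pressure may mean the tip is already epidural, subdural or intrathecal, so a needle through the dura before the syringe is pressurised may give no signal. Finally, Figure 6 and the CRF are not available here, so a signal field or clarifying rule in them cannot be excluded.

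**Conclusion.** The point holds in a limited form. The false-positive definition lacks a limb that the primary endpoint has, and the recording waiver usually removes the count in the same subjects. The endpoint can therefore understate wrong signals. The loss is confined to one secondary endpoint: the link between a puncture and a preceding signal. Dural puncture remains visible elsewhere when it is recognised.

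The size is small in absolute terms: about 0.1 to 2.2 punctures in the trial if the introduction's rates apply to this device, of which an unknown share followed a signal. In the illustration the reported rate is about 3 percentage points too low, which rests on the assumed 6 and 2 subjects. The documents do not support a claim that the arms would be ranked wrongly. A correction is still worthwhile, because it settles what the endpoint counts and costs little.

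**What to change.** 1. In 5.2.5, 5.2.5.1 and 7.2, add a third limb: a visual signal followed by dural puncture or subarachnoid catheter placement, whenever identified, where the needle was not advanced after the signal. Tie all three limbs to a visual signal, so that the sections agree.
2. For every dural puncture, record whether a signal came before or at the puncture (yes/no). Section 5.2.5 already has the procedure filmed, so this can be read from the video. Do not count punctures without a signal as false positives.
3. Keep the false-positive count for puncture subjects in the analysis, as an exception to the recording waiver in 5.2.5.
4. In 8.4.2, report false positives by arm with and without signal-associated punctures.

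The cost is wording in these sections and one CRF item, with no new procedure. The reported false-positive rate may be slightly higher, and a signalled puncture then appears in both the primary and this secondary endpoint. Reporting with and without these punctures keeps that overlap visible.

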8. STATISTICAL METHODS

8.1. Planned Sample Size

Considering the recommendation given by Lancaster, Dodd &Williamson. A total of 60 subjects (30 subjects per group) will be required in this study to obtain parameters such as ratio, mean and standard deviation which will be used in a sample size calculation for the full-scale trial, and to estimate the rate of participants who drop out of the trial.

8.2. Analysis Population

Intent-to-Treat (ITT) Population: The ITT will consist of all participants who are randomly assigned

to receive study device and have received any study device, irrespective of their protocol adherence. All analyses using the ITT will group participants according to randomized treatment. The ITT will be used as the efficacy analysis set.

Safety Set: The safety set will consist of all participants who received any study device. All analyses using the safety set will group participants according to treatment actually received.

8.3. Demographics and Other Baseline Characteristics

Demographics and other baseline characteristics will be summarized by descriptive statistics for two treatment groups. For continuous variables, the number, mean, standard deviation, median, minimum, and maximum values will be presented. A two sample independent t-test will be performed for continuous variables. For categorical variables, the numbers and percentages of subjects in each class will be listed, and the Fisher's exact test for testing two treatment group comparison.

8.4. Efficacy Assessment

Statistical analyses will be reported using summary tables, graphs, and data listings. Analysis are performed with SPSS, Version 20.0 (IBM Corporation, Armonk, NY, USA). The analysis population will be summarized by A and S groups. For categorical variables, frequencies and percentages will be summarized; continuous data will be shown as descriptive statistics. The variables within a normal distribution will be compared using Student's t-tests, and those without a normal distribution will be compared using the Mann-Whitney U test. The number of patients will be compared between the groups using the Fisher's exact test. All information will be summarized and presented in statistical analysis tables. As for data of efficacy and safety variables, no imputation method is applied.

8.4.1. Analysis of primary endpoint

The primary endpoint is the success of epidural localization. The primary analysis will be conducted by Fisher's exact test.

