The trial quantity of EpiFaith syringe were finished, as well as the biocompatibility testing to ISO 10993, the connector testing to ISO80369-7, epidural simulated testing on ex-vivo and in-vivo porcine spine were performed. Results of testing demonstrate that the EpiFaith syringe meets its performance specifications and is safe and effective for its intended use.

The aim of this study is to evaluate using the EpiFaith syringe with two different sensing medians for epidural localization. The hypothesis of the study is that EpiFaith syringe can detect LOR of epidural space effectively with its achievable pressure. It is beneficial to both junior and senior physicians by transforming the process into a safe and convenient procedure.

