2. OBJECTIVE

The objective of the study is to verify the efficacies of both air and saline based procedure of EpiFaith syringe for assisting the needle localization of the epidural space.

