3.4. Method of Assigning Subjects to Treatment Groups

Subjects will be randomized to one of the two groups (A group – EpiFaith syringe with air or S group – EpiFaith syringe with saline) at the ratio of 1:1. The randomization method will result in sealed, opaque envelopes containing the computer- generated, random assignment. Randomization will occur in blocks so that blocks of equal numbers of subjects will be used to avoid potential runs of assignments. The randomization code will be generated specifically for each center.

Screening number will be assigned once subject signed the inform consent. Only eligible subjects at Visit 2 will receive a randomization number at randomization. The subject will receive the

corresponding test devices assigned in the randomization envelope according to the randomization number. The number will be maintained by the investigator throughout the study. For any reason that a subject withdraws from the study prematurely after the randomization, his/her randomization number will not be reused. The next eligible subject will receive the lowest available randomization number.

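### The only primary analysis is a Fisher's test of air against saline, which cannot show how often either procedure succeeds, and no confidence interval is planned for the success proportions or their difference

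*Combined protocol and SAP*

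**What the plan says.** Section 8.4.1 names success of epidural localization as the primary endpoint and designates one analysis for it: "The primary analysis will be conducted by Fisher's exact test". Section 8.4 (repeated in the Synopsis, IX. Statistics, item 4) shows what the test compares: "The number of patients will be compared between the groups using the Fisher's exact test". Section 3.4 defines the groups as "A group – EpiFaith syringe with air or S group – EpiFaith syringe with saline", so the same device is used in both and no arm uses a different syringe.

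Section 8.4 also plans descriptive output by group: "For categorical variables, frequencies and percentages will be summarized". Success will therefore be reported as a count and a percentage in each arm. Neither the synopsis statistics nor Sections 8.1 to 8.5 mention a confidence interval, a target precision, a minimum success rate or a one-sample test.

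The purpose is stated in three places:
- Section 2 sets out to "verify the efficacies of both air and saline based procedure of EpiFaith syringe".
- Section 1 says: "The hypothesis of the study is that EpiFaith syringe can detect LOR of epidural space effectively".
- Section 8.1 justifies 30 subjects per group as a means "to obtain parameters such as ratio, mean and standard deviation which will be used in a sample size calculation for the full-scale trial".

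**The concern.** The three statements of purpose ask how well localization works with the device in each medium, and how well the study can estimate that. The designated primary analysis asks a different question: whether the two media differ. Because both arms use the same device, a p-value from that comparison would be the same whether the syringe did uniformly well or uniformly badly.

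If the plan is followed as written, the headline result cannot support or undermine the objective. The part of the report that does bear on it, the percentage in each arm, would come with no planned statement of its uncertainty, which at 30 per arm is considerable.

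**Working it through.** **Inputs.** From the documents: 30 subjects per group, 60 in total (Section 8.1); 1:1 allocation (Section 3.4); a binary primary endpoint (Section 7.1). Assumed, because the documents do not give them: two-sided 5% significance, 95% intervals, all 30 subjects per arm evaluable, and the success counts used below.

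**The plan's own figure.** 2 × 30 = 60, which agrees with 1:1 allocation. No significance level, power, effect size or target precision is stated, so there is no sample-size formula to reproduce.

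**Step 1: does Fisher's p-value respond to the level of success?** The two-sided p-value sums the probabilities of all tables, given the margins, that are no more likely than the one observed. When the two counts are equal, the observed table is the most likely one, so every table is included and p = 1. At 30/30 v 30/30 only one table is possible, so again p = 1. The per-arm column is the Clopper-Pearson interval: the lower limit is the 2.5% quantile of Beta(x, n−x+1), and the upper limit is the 97.5% quantile of Beta(x+1, n−x). At 30/30 the lower limit reduces to 0.025^(1/30) = 0.884.

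| Air v saline | Fisher p | Success in each arm | Exact 95% CI in each arm |
|---|---|---|---|
| 15/30 v 15/30 | 1.0 | 50% | 31.3–68.7% |
| 27/30 v 27/30 | 1.0 | 90% | 73.5–97.9% |
| 28/30 v 28/30 | 1.0 | 93.3% | 77.9–99.2% |
| 30/30 v 30/30 | 1.0 | 100% | 88.4–100% |

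The p-value is identical in every row, while the intervals for 15/30 and 30/30 do not even overlap.

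**Step 2: how precisely is the difference estimated?** Newcombe's interval uses the Wilson limits of each arm, (x + z²/2 ± z√(x(n−x)/n + z²/4)) / (n + z²) with z = 1.96. These are 78.7% and 98.2% for 28/30, and 55.6% and 85.8% for 22/30.

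- 28/30 v 28/30: the difference is 0. Each limit lies √((0.933−0.787)² + (0.982−0.933)²) = 0.154 from zero, so the interval is −15.4 to +15.4 points.
- 28/30 v 22/30: the difference is 20 points.
  - Lower limit: 0.200 − √((0.933−0.787)² + (0.858−0.733)²) = +0.7 points.
  - Upper limit: 0.200 + √((0.982−0.933)² + (0.733−0.556)²) = +38.4 points.

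**Step 3: can the interval and the test disagree?** In the second case there are 10 failures among 60 subjects, split 2 and 8. The probability of 2 or fewer failures in the first arm is [C(30,2)·C(30,8) + C(30,1)·C(30,9) + C(30,0)·C(30,10)] / C(60,10) = 0.0338 + 0.0057 + 0.0004 = 0.0399. Doubling by symmetry gives p = 0.080. The Newcombe interval excludes zero while Fisher's test does not reach 0.05, so the two can point in different directions.

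**Step 4: what would a non-significant result mean?** Exact power, by enumeration of all 31 × 31 outcomes with 30 per arm, is 9% for true rates of 95% v 85%, 24% for 95% v 80% and 44% for 95% v 75%. Failure to reach 0.05 would be the more likely outcome in all three cases.

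**The case against.** The strongest reply is that the study is randomised between two media and that Section 1 states its purpose accordingly: "The aim of this study is to evaluate using the EpiFaith syringe with two different sensing medians for epidural localization". A between-group test suits that contrast, Fisher's test is a sound choice at this size, and the single-sentence objective can be read as comparative. Group percentages are already planned, so anyone can compute an interval from the counts later and no data are lost.

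Much of this stands. The test is valid for the comparison and should be kept, and the mismatch is not a flat contradiction in the text. The reply does not explain why the comparison should be the only primary analysis when the hypothesis in Section 1 concerns the device's effectiveness and Section 8.1 sizes the study for estimation. Computing intervals afterwards also leaves the method, and the result that leads, to be chosen once the data are known. The 28/30 v 22/30 case shows that this choice can matter.

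A reader might infer more than the documents support:
- *That success per arm will go unreported.* It will be reported, as counts and percentages.
- *That the ratio will enter the full-scale calculation without regard to its uncertainty.* Section 8.1 says that it will be used, not how. All that can be said is that no measure of uncertainty is planned here.
- *That a non-significant result will be presented as showing the media to be alike.* No readable text says so. The hypothesis-type boxes in the Synopsis (IX. Statistics, item 1) cannot be read, and nothing here rests on them.

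**Conclusion.** The concern holds as a cheap improvement. The sole designated primary analysis gives no information on the level of success in either arm, and the readable plan provides no measure of precision for the per-arm proportions or their difference. At 30 per arm the omission is not trivial: even 28/30 leaves a per-arm interval about 21 points wide (99.2 − 77.9 = 21.3), and equal results of 28/30 leave the difference uncertain by 15.4 points either way.

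That Fisher's p-value is unaffected by a shared success level is a property of the test and needs no assumption about rates. The interval widths rest on the assumed counts, 30 evaluable subjects per arm and a 95% level. The power figures and the p = 0.080 disagreement also assume a 5% two-sided threshold, which the plan does not state. None of this shows that 60 subjects is the wrong number for a pilot, or that Fisher's test is the wrong test for comparing the media.

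**What to change.** In Section 8.4.1, and in the matching text of the Synopsis (IX. Statistics, item 4):

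1. Make the primary result the success proportion in each arm with an exact (Clopper-Pearson) 95% confidence interval.
2. Report the air–saline difference with a 95% confidence interval by a method named in advance, for example Newcombe.
3. Keep Fisher's exact test as the supporting comparison between media, and state beforehand which result leads if the interval and the test disagree.
4. As a precaution, state that p > 0.05 will not be read as showing that the media are alike.

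The objective can stay as worded. The cost is a few sentences and a few extra table columns, with no additional patients or data. Every interval follows from the counts, so it can be computed in any software. The drawbacks are a primary result that looks less definite than a single p-value, and the need to settle the order of precedence in item 3 before the data are seen.

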8.5. Safety Assessment

Incidence of the adverse events will be summarized. In the case of CTCAE grade summaries, the most severe event will be presented in summary tables in the case of multiple occurrences per patient. The frequency and the percentage of each category will be presented. All safety parameters, including adverse events, adverse device effect, serious adverse event, serious adverse device effects and unanticipated adverse device effect will be listed by A and S groups. The Medical Dictionary for Regulatory Activities (MedDRA) adverse event dictionary will be used to map verbatim adverse events to preferred terms and system organ class. Fisher's exact test will be applied for comparing the incidences of adverse events between treatment groups.

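### Optional, low-cost improvement: at about 30 per arm Fisher's exact test is valid but conservative, and Boschloo's exact test holds the same assumed 5% cap with more power

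*Combined protocol and SAP*

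**What the plan says.** Section 8.4.1 of the protocol states: "The primary endpoint is the success of epidural localization". It then gives one sentence of method: "The primary analysis will be conducted by Fisher's exact test". Section 8.4 names Fisher's test generally for comparing numbers of patients between the groups, and SPSS 20.0 as the software. For safety, section 8.5 says "Fisher's exact test will be applied for comparing the incidences of adverse events between treatment groups". The Synopsis (IX.4) repeats the general and the safety sentences.

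Allocation is "at the ratio of 1:1" (section 3.4). On size, section 8.1 says "A total of 60 subjects (30 subjects per group) will be required in this study to obtain parameters such as ratio, mean and standard deviation", to feed the sample size calculation of a later full-scale trial and to estimate dropout. Section 3.2.1 recruits approximately 60 subjects. The efficacy set is the ITT set, which requires that the subject received a study device (section 8.2), and nothing is imputed (section 8.4).

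The plan gives no significance level, sidedness, power target, expected success or event rate, or difference of interest. It mentions no unconditional exact test.

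**The concern.** The design fixes the two group sizes but not the total number of successes. Fisher's test conditions on that total. When successes are near 100%, or events near 0%, each total allows only a few distinct tables, and the attainable significance levels are coarse. The true error rate then falls far below the nominal one, and power falls with it.

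Boschloo's test takes Fisher's p-value as its statistic and computes the error rate over both binomial samples, at the worst common success rate. It therefore keeps the nominal cap while using more of it. What is at stake is some sensitivity in the one primary comparison and in the comparison of adverse-event incidence between air and saline, in a study with only 60 subjects.

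**Working it through.** **Plan's own figure.** 2 x 30 = 60, as section 8.1 states. No power formula can reproduce it, because the plan gives no level, power, rates or difference.

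**Inputs.** From the documents: Fisher's test (8.4.1, 8.5), 30 per group (8.1), 1:1 (3.4). Assumed: two-sided 5%, no loss from either arm, and the success rates tabulated below. By symmetry an event rate of q gives the same results as a success rate of 1 - q.

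**Formulas.** Let (x, y) be the successes out of 30 in each arm.
- Fisher: p_F(x, y) is the sum, over tables with the same total x + y, of the hypergeometric probabilities no larger than the observed one. Reject if p_F <= 0.05.
- Boschloo: p_B(x, y) is the maximum over π of Σ b(i; 30, π) b(j; 30, π), summed over all tables (i, j) with p_F(i, j) <= p_F(x, y). Reject if p_B <= 0.05.
- Size at a common rate π, and power at rates (π1, π2), are binomial sums over the rejection region.

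**One table by hand.** For 30/30 v 25/30, all five failures are in one arm: C(30,5)/C(60,5) = 142,506/5,461,512 = 0.0261. The mirror table is equally probable, so p_F = 2 x 0.0261 = 0.0522. Boschloo's p-value is 0.0274. The table 0/30 v 5/30 events gives the same two values.

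**All 31 x 31 = 961 tables at 30 v 30.** Fisher rejects 546. Boschloo rejects 578, including all 546.

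| Common success rate | Fisher size | Boschloo size |
|---|---|---|
| Maximum over all rates | 2.74% | 4.69% |
| 80% | 2.22% | 3.14% |
| 90% | 0.94% | 2.33% |
| 95% | 0.15% | 0.71% |
| 98% | 0.003% | 0.03% |

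| Success rates | Fisher power | Boschloo power |
|---|---|---|
| 95% v 90% | 1.9% | 4.8% |
| 95% v 85% | 9.3% | 16.2% |
| 95% v 80% | 24.1% | 33.5% |
| 90% v 70% | 37.2% | 42.5% |
| 98% v 80% | 40.5% | 55.1% |
| 99% v 85% | 23.1% | 38.7% |

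For adverse events, 2% v 15% gives 18.4% against 31.3%, 2% v 10% about 4% against 10%, and 1% v 5% 0.2% against 1.2%.

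**Other levels.** For 95% v 80% at 30 v 30, Fisher then Boschloo: 7.5% then 13.6% at level 0.01; 18.4% then 22.3% at 0.025; 36.4% then 50.4% at 0.10.

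**Unequal arms.** The same enumeration at 28 v 30:
- Size at 95% success is 1.2% for Fisher and 1.5% for Boschloo, so the contrast nearly vanishes.
- For 95% v 80%, if the 28-subject arm is the better one, power goes from 25.5% to 35.4%. If the 30-subject arm is better, it goes from 40.2% to 40.9%.
- For 99% v 85% the gain is about 16 points in the first direction and nil in the second.

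One extra subject can also move a borderline table. For 0/31 v 5/30, the observed table has probability C(30,5)/C(61,5) = 142,506/5,949,147 = 0.0240. Its opposite has C(31,5)/C(61,5) = 169,911/5,949,147 = 0.0286, which is larger and so is not added. Fisher's p-value is then 0.024, already below 0.05. If the extra subject is in the other arm (0/30 v 5/31), both terms count and p_F = 0.0240 + 0.0286 = 0.0525 after rounding.

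**The case against.** Fisher's test is valid, prespecified and available in the named software. In a randomised comparison, conditioning on the total has its own justification, and calling the test dominated presupposes that unconditional error is the criterion. All of that stands, and it is why this is not an error in the plan. It does not defeat the change, because Boschloo's test orders tables by Fisher's own p-value and Fisher's result can be printed beside it.

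A reader might infer more than the documents support:
- **That planned power is being lost.** None is planned. Section 8.1 justifies 60 subjects by estimation for a later trial.
- **That the trial's conclusion turns on p = 0.052 against 0.027.** The plan attaches no level, decision rule or progression criterion to the p-value. Section 8.4 also requires frequencies and percentages by group. The early-termination trigger in section 6.2 is a count of dural punctures, not a test result.
- **That harm signals will be missed.** Section 8.5 lists all safety parameters by group, so a 0 v 5 split is visible without a test. For rare events, power is very low under either test.
- **That the 30 v 30 contrasts are what the trial will show.** Recruitment is approximate and the ITT set can drop randomised subjects who received no device. The 28 v 30 results show how much two subjects matter.

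A further fair point is that, for a pilot, an interval for the difference matters at least as much as the choice of test. With 90% in both arms the Wald 95% half-width is 1.96 x √(2 x 0.9 x 0.1/30) = 0.152, about 15 points.

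**Conclusion.** The point holds as an optional refinement. At 30 v 30 and an assumed two-sided 5%, Boschloo's test keeps the error cap (4.7% at most, against 2.7% for Fisher) and adds about 3 to 16 points of power over the pairs tabulated. The direction is the same at levels 0.01, 0.025 and 0.10, and in equal arms of 27, 28, 29 and 31. The size of the gain is not stable: at 28 v 30 it depends on which arm does better and can be close to nothing. Boschloo recovers only part of the loss. It is itself conservative at very high success, and detecting small differences stays out of reach. The level, the rates and the arm sizes after losses are assumptions; the plan supplies only 30 per group.

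**What to change.** Before the data are analysed, name the two-sided Boschloo exact unconditional test in section 8.4.1 for success and in section 8.5 for overall adverse-event incidence. State its significance level and the validated software routine. Bring the general sentence in section 8.4 and the matching Synopsis text (IX.4) into line. Report Fisher's p-value alongside. The timing matters: a switch made after seeing a borderline Fisher result would not be credible.

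The cost is a few sentences and an exact routine in software other than SPSS 20.0. No subjects, visits or data change. Fisher's test would remain for the baseline comparisons (8.3) and the secondary count endpoints (8.4.2) unless those are changed too, so the plan would either mix tests or need those sections edited as well.
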